5.1 Number of Subjects

- Part A: approximately 27 patients
- Part B: approximately 12 patients in no more than 2 dose levels
- Part C: approximately 60 patients in no more than 2 dose cohorts, with 30 patients at the most in one dose cohort

5.2 Inclusion Criteria

1. Patients must understand and voluntarily sign the Informed Consent Form (ICF).
2. Patients \geq 18 years.
3. Provision of blood sample to test ESR1 mutation status and for other biomarker assessment. In part A/B, the ESR1 mutation status will be tested retrospectively; In part C, only the patients with ESR1 mutation positive is eligible (See Appendix 6).
4. Documented positive oestrogen receptor status of primary or metastatic tumour tissue, according to the local laboratory parameters. HER-2 negative. These laboratory parameters are consistent with accepted diagnostic guidelines such as the American Society of Clinical Oncology (ASCO) / College of American Pathologists (CAP) Clinical Practice Guideline for Pathologists estrogen (ER) and progesterone receptor (PgR) testing in breast cancer ([Allison et al., 2020](#)).
5. Menopausal women according to one of the following criteria:
 - Prior bilateral ovariectomy;
 - Patients \geq 60 years of age;
 - Patients $<$ 60 years of age presenting an amenorrhea of more than 12 months and follicle stimulating hormone (FSH) and plasma estradiol levels within the postmenopausal range as assessed by the local laboratory in the absence of chemotherapy, tamoxifen, tolimifene, or ovarian castration in the past 1 year, and no oral contraceptives, hormone replacement therapy, or gonadotropin-releasing hormone agonist or antagonist;
 - Patients $<$ 60 years of age who are taking either tamoxifen or tolimifene with two consecutive FSH and estradiol levels in the postmenopausal range.
 - Or premenopausal or perimenopausal female subjects but must be willing to receive and maintain an approved luteinizing hormone-releasing hormone(LHRH) agonist during the study treatment period (LHRH agonist treatment initiated 28 days prior to the first study drug treatment); or for males: willing to receive and

maintain an approved LHRH agonist during the study treatment period (LHRH agonist treatment initiated 28 days prior to the first study drug treatment).

6. Previous therapy failed or intolerable, or standard therapy not available:

Part A/C: Previous therapy failed or intolerable, or standard therapy not available.

Part B/C: Patients should have received at least 1 line ET, or received no more than 1-line systematic chemotherapy for advanced/metastatic disease, no more than 1 target therapy.

7. Patients who are HIV positive with CD4+ T-cell counts ≥ 350 cells/uL may be eligible.
8. Eastern Cooperative Oncology Group (ECOG) performance status of 0 or 1.
9. At least one measurable lesion according to RECISTv1.1 criteria.
10. Life expectancy ≥ 12 weeks.
11. Adequate organ and bone marrow function (no use of hematopoietic stimulating factor, no blood transfusion or human albumin within 7 days prior to screening):
- Blood routine: Absolute neutrophil count (ANC) $\geq 1.5 \times 10^9/L$; Platelet count (PLT) $\geq 100 \times 10^9/L$; Hemoglobin (HGB) ≥ 90 g/L;
 - Liver function: Serum Total bilirubin (TBIL) ≤ 1.5 Upper limit of normal value (ULN); Alanine aminotransferase (ALT) and Aspartate transferase (AST) $\leq 3 \times ULN$ in subjects without liver metastasis; ALT or AST $\leq 5 \times ULN$ with liver metastasis;
 - Renal function: Serum creatinine $\leq 1.5 \times ULN$ or estimated creatinine clearance (CLcr) ≥ 60 mL/min as calculated using Cockcroft-Gault formula;
 - Coagulation function: Activated Partial thromboplastin Time (APTT) and international normalized ratio (INR) $\leq 1.5 \times ULN$ (or within target range if on anticoagulation therapy);
 - Cardiac function: Echocardiography (ECHO) shows left ventricular ejection fraction (LVEF) $> 50\%$.
12. Women of childbearing potential must have a negative serum pregnancy test within 7 days prior to the first dose. Female patients of childbearing potential must agree to use effective methods of contraception from the time of signature of informed consent, throughout the study and for 6 months after the last dose of the investigational product, like double barrier methods, condoms, oral or injectable contraceptives, intrauterine devices, etc. All female subjects will be considered to be of childbearing potential

unless they are postmenopausal, postmenopausal, or sterilized (hysterectomy, tubal resection).

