6. Previous therapy failed or intolerable, or standard therapy not available:

Part A: Previous therapy failed or intolerable, or standard therapy not available.

Part B/C: Patients should have received at least 1 line ET, or received no more than 1-line systematic chemotherapy for advanced/metastatic disease, no more than 1 target therapy.

	
 7. Eastern Cooperative Oncology Group (ECOG) performance status of 0 or 1(See Appendix 6). 8. At least one measurable lesion according to RECISTv1.1 criteria. 9. Life expectancy \geq 12 weeks. 10. Adequate organ and bone marrow function (no use of hematopoietic stimulating factor, no blood transfusion or human albumin within 7 days prior to screening): 
 a) Blood routine: Absolute neutrophil count (ANC) \geq $1.5 \times 10^9/L$; Platelet count (PLT) \geq $100 \times 10^9/L$; Hemoglobin (HGB) \geq 90 g/L; b) Liver function: Serum Total bilirubin (TBIL) \leq 1.5 Upper limit of normal value (ULN); Alanine aminotransferase (ALT) and Aspartate transferase (AST) \leq 3\timesULN in subjects without liver metastasis; ALT or AST \leq 5\timesULN with liver metastasis; c) Renal function: Serum creatinine \leq 1.5\timesULN or estimated creatinine clearance (CLcr) \geq 60 mL/min as calculated using Cockcroft-Gault formula; d) Coagulation function: Activated Partial thromboplastin Time (APTT) and international normalized ratio (INR) \leq 1.5\timesULN (or within target range if on anticoagulation therapy); e) Cardiac function: Echocardiography (ECHO) shows left ventricular ejection fraction (LVEF) > 50%. 11. Women of childbearing potential must have a negative serum pregnancy test within 7 days prior to the first dose. Female patients of childbearing potential must agree to use effective methods of contraception from the time of signature of informed consent, throughout the study and for 6 months after the last dose of the investigational product, like double barrier methods, condoms, oral or injectable contraceptives, intrauterine devices, etc. All female subjects will be considered to be of childbearing potential unless they are postmenopausal, postmenopausal, or sterilized (hysterectomy, tubal resection).

Exclusion Criteria
	
 1. Documented medical history or ongoing gastrointestinal disease (Including difficulty in swallowing capsules, Crohn's disease,

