	
ulcerative colitis, or short bowel syndrome) or other malabsorption that may affect the absorption of oral study drug.
 
2. Participated in other clinical trials of investigational drugs or investigational devices within 4 weeks before the first medication; or received chemotherapy, targeted therapy, immunotherapy and clinical trial medication and other anti-tumor treatment within 4 weeks, or received radiotherapy, endocrine drugs or Chinese traditional medicines with anti-tumor indications 2 weeks prior to the first dose, Or receive mitomycin and nitrosourea within 6 weeks prior to the first dose3. The toxicity of previous anti-tumor treatment has not recovered to grade 0 or 1 (except for alopecia, chemotherapy-induced peripheral neurotoxicity \leq grade 2).4. Major surgical surgery (except biopsy) or incomplete healing of the surgical incision within 4 weeks prior to the first study drug treatment.5. Known other malignant tumors within 2 years before enrollment (except for cervical carcinoma insitu, superficial noninvasive bladder tumors, breast ductal carcinoma in situ, prostatic intraepithelial neoplasia without evidence of prostate cancer, or curatively treated Stage I nonmelanoma skin cancer);6. Subjects with unstable or symptomatic or progressive Central nervous system (CNS) metastasis. Subjects with a history of brain metastases who were clinically stable and who underwent Magnetic resonance imaging (MRI) or Computed tomography (CT) Subjects with CT (if not suitable for MRI) who confirm no CNS disease progression can be enrolled (MRI or CT must be performed at least 4 weeks after the last brain radiotherapy).7. Previous history of interstitial lung disease, drug-induced interstitial lung disease, symptomatic interstitial lung disease or any evidence of active pneumonia on chest CT scan within 4 weeks prior to the first study drug treatment;8. Known to interfere with the test requirements of mental illness or drug abuse disease;9. History of human immunodeficiency virus HIV infection, or active bacterial or fungal infection requiring systemic treatment within 14 days prior to the first study drug treatment.
--	--

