6. Vital signs include temperature, pulse, breathing and blood pressure. On C0D1 and C1D1, the vital signs will be measured at pre-morning dose(s), and 0.5 h, 2 h, 4 h, 8 h, 12 h and 24 h after the morning dose(s). On C0D3, C0D4, C1D8, C1D15, C1D22, C2D1, C2D15, (C3~Cn) D1, the vital signs will be measured at pre-morning dose(s). Other examinations may be conducted if deemed clinically necessary by the investigator.
7. 12-lead ECG will be performed three times at Screening, 30 min, 20 min and 10 min pre-dose and 0.5 h, 1 h, 1.5 h, 2 h, 3 h, 4 h, 5 h, 6 h, 8 h, 12 h and 24 h post-dose on C0D1 and C1D1, and the spacing between each ECG examination will be at least 1 min. On C1D8, C1D15, C1D22, C2D1, C2D15, (C3~Cn) D1, the 12-lead ECG will be measured at pre-morning dose(s) and 2 h after the morning dose(s). Meanwhile, 12-lead ECG will be performed on prematurely withdrawn. If QTcF > 450 ms (male) or > 470 ms (female), 3 consecutive ECGs should be collected to calculate the mean QTcF value.
8. Human immunodeficiency virus antibody, hepatitis B surface antigen, hepatitis B core antibody, hepatitis C virus antibody, and Treponema pallidum antibody. period and may optionally be done at additional time points depending on investigator discretion.
9. Only applicable to women of childbearing age; Subjects must have a negative blood pregnancy test during the screening period. Pregnancy tests will be performed anytime during the course of the study, as per investigator's discretion. Serum or urine tests are acceptable based on the site's standard clinical practice, if a urine pregnancy test is positive, it must be confirmed by a serum pregnancy test.
10. Infectious disease screening includes polymerase chain reaction for SARS-CoV-2;
11. Blood will be collected for PK analysis of the FWD1802 Tablet and/or its metabolites (if any), details please refer to 7.5.1 PK Samples.
12. Tumor assessment: All patients will undergo MRI, chest, abdomen, pelvis and bone examination at baseline period, and subsequent imageological examination included the chest, abdomen, pelvis, and other metastatic sites, if any. The preferred

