5.3 Exclusion Criteria

1. Documented medical history or ongoing gastrointestinal disease (Including difficulty in swallowing capsules, Crohn's disease, ulcerative colitis, or short bowel syndrome) or other malabsorption that may affect the absorption of oral study drug.
2. Participated in other clinical trials of investigational drugs or investigational devices within 4 weeks before the first medication; or received chemotherapy, targeted therapy, immunotherapy and clinical trial medication and other anti-tumor treatment within 4 weeks, or received radiotherapy, endocrine drugs or Chinese traditional medicines with anti-tumor indications 2 weeks prior to the first dose. Or receive mitomycin and nitrosourea within 6 weeks prior to the first dose.
3. The toxicity of previous anti-tumor treatment has not recovered to grade 0 or 1 (except for alopecia, chemotherapy-induced peripheral neurotoxicity \leq grade 2).
4. Major surgical surgery (except biopsy) or incomplete healing of the surgical incision within 4 weeks prior to the first study drug treatment.
5. Known other malignant tumors within 2 years before enrollment (except for cervical carcinoma insitu, superficial noninvasive bladder tumors, breast ductal carcinoma in situ, prostatic intraepithelial neoplasia without evidence of prostate cancer, or curatively treated Stage I nonmelanoma skin cancer);
6. Subjects with unstable or symptomatic or progressive Central nervous system (CNS) metastasis. Subjects with a history of brain metastases who were clinically stable and who underwent Magnetic resonance imaging (MRI) or Computed tomography (CT) Subjects with CT (if not suitable for MRI) who confirm no CNS disease progression can be enrolled (MRI or CT must be performed at least 4 weeks after the last brain radiotherapy).;
7. Previous history of interstitial lung disease, drug-induced interstitial lung disease, symptomatic interstitial lung disease or any evidence of active pneumonia on chest CT scan within 4 weeks prior to the first study drug treatment;
8. Known to interfere with the test requirements of mental illness or drug abuse disease;
9. History of human immunodeficiency virus HIV infection, or active bacterial or fungal infection requiring systemic treatment within 14 days prior to the first study drug treatment.
10. Presence of active syphilis infection.

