7.3 Description of Assessments

7.3.1 Laboratory Assessments

All protocol required clinical laboratory assessments should be performed at the investigational site's local laboratory. All clinical laboratory results must be documented on the CRF and reference ranges and safety parameters must be provided for each laboratory used. The following assessments will be performed and evaluated during the study.

Table 10 Laboratory Assessments

Hematology	red blood cell counts (RBC), white blood cell counts (WBC), and differential counts (neutrophils (NE), lymphocytes (LY#), monocytes (MO#), eosinophils (EO#), and basophils (BA)), platelet count (PLT), hemoglobin (HGB), and hematocrit (HCT)
Coagulation Function	PT (Prothrombin Time), APTT (Partial Thromboplastin Time), INR (International Normalized Ratio), Thrombin time (TT) and fibrinogen (FIB)
Fasting Serum Biochemistry	ALT, AST (Aspartate Transaminase), GGT (Gamma-glutamyl Transpeptidase), TBIL (total bilirubin), DBIL (direct bilirubin), BUN (Urea Nitrogen) or urea, Cr (Creatinine), UA (uric acid), GLU (blood glucose), potassium, sodium, chlorine, calcium, phosphate, magnesium, TP (total protein), ALB (albumin), albumin/globulin ratio, LDH (Lactate Dehydrogenase), TBA (Total Bile Acid), TG (Triglyceride), CK (Creatine kinase), CK-MB (creatinine kinase isoenzyme) and ALP (Alkaline Phosphatase).

Pregnancy Test	serum β -Human Chorionic Gonadotropin (β -HCG). Lack of childbearing potential must be noted in the source documents, if applicable.
Urinalysis	specific gravity, pH, white blood cells, red blood cells, α 1 microglobulin, β macroglobulin, occult blood, proteins and glucose.
Infectious Disease Screening	HCV, HBV, HIV, syphilis, etc., but if the subject can present the test results done within 4 weeks prior to the administration, the screening can be exempted.

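### HIV-positive patients with CD4+ counts of at least 350 cells/uL are allowed by inclusion 7 but barred by exclusion 9, and the protocol does not say which governs

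*Protocol*

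**What the plan says.** Three places in the protocol set the HIV rule.

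- Section 5.2, inclusion 7: "Patients who are HIV positive with CD4+ T-cell counts" of at least 350 cells/uL may be eligible.
- Section 5.3, exclusion 9: "History of human immunodeficiency virus HIV infection, or active bacterial or fungal infection requiring systemic treatment within 14 days" before first study treatment. The HIV limb carries no CD4+ condition and does not refer to inclusion 7.
- Synopsis: exclusion 9 has the same wording as Section 5.3. The inclusion list has no HIV item; its criterion 7 is ECOG performance status, which is criterion 8 in Section 5.2.

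HIV status is part of screening in all three parts. Footnote 8 to each schedule of events (Tables 1 to 3) lists "Human immunodeficiency virus antibody, hepatitis B surface antigen, hepatitis B core antibody, hepatitis C virus antibody, and Treponema pallidum antibody". Table 10 in Section 7.3.1 gives the infectious disease panel as "HCV, HBV, HIV, syphilis, etc., but if the subject can present the test results done within 4 weeks prior to the administration", in which case the screening test can be waived. Neither place names a CD4+ count.

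**The concern.** Anyone who is HIV positive has a history of HIV infection. Read as written, exclusion 9 therefore removes every patient whom inclusion 7 was written to let in. Both sentences are operative criteria in the same version of the protocol, and the synopsis agrees with only one of them.

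What is at stake is uniform eligibility in a multicentre first-in-human trial. A site that works from inclusion 7 could enrol a patient whom another site, working from exclusion 9 or the synopsis, would turn away. If the patient is enrolled, the record shows an eligibility deviation that the protocol itself invited.

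**Working it through.** No arithmetic applies. The check is to apply each criterion to each type of patient.

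| Patient | Inclusion 7 (Section 5.2) | Exclusion 9 (Section 5.3 and synopsis) | Result |
|---|---|---|---|
| HIV positive, CD4+ ≥ 350 cells/uL | may be eligible | excluded | conflict |
| HIV positive, CD4+ < 350 cells/uL | not admitted | excluded | no conflict |
| HIV negative | not relevant | HIV limb not relevant | no conflict |

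The conflict lies in the first row only.

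**Could the 14-day treatment window in exclusion 9 apply to HIV as well?** The opening words about history, and the comma after the HIV limb, make this unlikely. Even on that reading a conflict remains for an HIV-positive patient with CD4+ ≥ 350 who needs systemic treatment in the window, because inclusion 7 has no treatment condition.

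**Is an exception implied?** Exclusion 11 in the same list spells out its exceptions for hepatitis B and C. Exclusion 9 has none.

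**Is there a precedence rule?** None is stated. Sections 7.4 and 7.4.1 tie enrolment and eligibility to the inclusion criteria and do not mention the exclusions. The schedules of events list inclusion and exclusion criteria as a single screening item.

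**Does the synopsis settle it?** No. It has 11 inclusion criteria against 12 in Section 5.2. The HIV item is the extra one, and the numbering shifts from item 7 onward. This adds a disagreement between synopsis and body.

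**Can inclusion 7 be applied as the assessments stand?** HIV antibody is tested or a recent result is accepted, so HIV status will be known. The CD4+ count that the criterion depends on is not named in footnote 8 or Table 10.

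**The case against.** The best defence is that, by ordinary practice, a patient must meet the inclusions and trigger no exclusion. Exclusion 9 would then govern, the synopsis agrees with it, and inclusion 7, which is only permissive, would have no effect. On that view there is one answer: the patient is excluded. This is a reasonable reading, but the protocol does not state it, and the enrolment text in Section 7.4 points to the inclusion criteria alone. Even if it is accepted, inclusion 7 remains as text telling sites the opposite of the rule in force.

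The defence is right to limit the point. A reader might infer any of four stronger claims, and the protocol supports none of them:

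- **That all HIV-positive patients are both admitted and barred.** Below 350 cells/uL the criteria agree.
- **That sites will enrol different populations.** The protocol gives no HIV prevalence and no site practice, so this is possible, not certain.
- **That the escalation data are at risk because one patient is a large share of a cohort.** In Part A cohorts of 1 to 6, one patient is 1/6 = 17% to 1/1 = 100%. That holds for any criterion and any single patient, and says nothing about DLT rates or the MTD. In the 60-patient Part C the same share is 1/60, under 2%.
- **That the conflict opens a drug-interaction gap through ritonavir- or cobicistat-containing regimens.** Exclusions 16 and 18 already address CYP3A and P-gp inhibitors, and Appendix 5 lists these products, whatever the HIV rule says.

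**Conclusion.** The contradiction is real and should be corrected. It covers HIV-positive patients with CD4+ counts of at least 350 cells/uL and nobody else. For them, Section 5.2 permits what Section 5.3 and the synopsis forbid, and nothing in the available text resolves it. Sites could decide differently, or an enrolment under inclusion 7 would be a deviation under exclusion 9.

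The size cannot be computed from the protocol. That few patients would be affected is an assumption, and no effect on the safety, dose-finding or efficacy results is shown. The conclusion rests on reading exclusion 9 as it is punctuated; the alternative reading narrows the conflict but does not remove it. Which rule is right is for the sponsor to decide.

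**What to change.** Reconcile Section 5.2 inclusion 7, Section 5.3 exclusion 9 and the synopsis into one HIV eligibility rule, worded consistently, so that no patient is both permitted and excluded. Bring the synopsis inclusion list and its numbering into line with Section 5.2 at the same time.

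The cost depends on the choice:

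- **No CD4+ threshold kept:** wording only.
- **CD4+ threshold kept:** exclusion 9 and the synopsis must carry the matching exception, and a CD4+ count must be added to the screening assessments (footnote 8 of Tables 1 to 3, and Table 10).

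Either way it is a protocol change, which under Section 12.2 goes to the IRB for review and approval. No statistical analysis or sample size is affected.

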5.3 Exclusion Criteria

1. Documented medical history or ongoing gastrointestinal disease (Including difficulty in swallowing capsules, Crohn's disease, ulcerative colitis, or short bowel syndrome) or other malabsorption that may affect the absorption of oral study drug.
2. Participated in other clinical trials of investigational drugs or investigational devices within 4 weeks before the first medication; or received chemotherapy, targeted therapy, immunotherapy and clinical trial medication and other anti-tumor treatment within 4 weeks, or received radiotherapy, endocrine drugs or Chinese traditional medicines with anti-tumor indications 2 weeks prior to the first dose. Or receive mitomycin and nitrosourea within 6 weeks prior to the first dose.
3. The toxicity of previous anti-tumor treatment has not recovered to grade 0 or 1 (except for alopecia, chemotherapy-induced peripheral neurotoxicity \leq grade 2).
4. Major surgical surgery (except biopsy) or incomplete healing of the surgical incision within 4 weeks prior to the first study drug treatment.
5. Known other malignant tumors within 2 years before enrollment (except for cervical carcinoma insitu, superficial noninvasive bladder tumors, breast ductal carcinoma in situ, prostatic intraepithelial neoplasia without evidence of prostate cancer, or curatively treated Stage I nonmelanoma skin cancer);
6. Subjects with unstable or symptomatic or progressive Central nervous system (CNS) metastasis. Subjects with a history of brain metastases who were clinically stable and who underwent Magnetic resonance imaging (MRI) or Computed tomography (CT) Subjects with CT (if not suitable for MRI) who confirm no CNS disease progression can be enrolled (MRI or CT must be performed at least 4 weeks after the last brain radiotherapy).;
7. Previous history of interstitial lung disease, drug-induced interstitial lung disease, symptomatic interstitial lung disease or any evidence of active pneumonia on chest CT scan within 4 weeks prior to the first study drug treatment;
8. Known to interfere with the test requirements of mental illness or drug abuse disease;
9. History of human immunodeficiency virus HIV infection, or active bacterial or fungal infection requiring systemic treatment within 14 days prior to the first study drug treatment.
10. Presence of active syphilis infection.

11. Subjects with known active hepatitis B virus (HBV) or hepatitis C virus (HCV) infection with abnormal liver function (Absence of infection was defined as HBsAg negative, HBV DNA negative and HCV antibody negative), except to:
 - Subjects who test positive for HBsAg or HBsAb during the screening period may be enrolled if the PCR test result for HCV-RNA is < 500 IU/ml (2000 copies/mL), but receive antiviral treatment according to the investigator's assessment and undergo PCR for HBV-DNA during the study treatment period;
 - Subject has a positive test for HCV antibody at screening and can be enrolled if the PCR test result for HCV-RNA is negative.
12. History of clinically significant cardiovascular disease, such as:
 - Symptomatic congestive heart failure according to New York Heart Association Grades (NYHA $>$ Grade 2);
 - Severe/unstable angina, new angina within last 3 months;
 - Myocardial ischemia and long-term use of drugs for control; according to NYHA, grade III-IV cardiac insufficiency;
 - Any event of acute myocardial infarction within 6 months before screening;
 - Any grade ≥ 2 supraventricular arrhythmia or ventricular arrhythmia requiring treatment or intervention;
 - Any grade atrial fibrillation, coronary/peripheral artery bypass graft, or cerebrovascular symptoms including transient ischemic attack;
 - QTcF (Fridericia's correction formula used) > 470 ms;
 - ECG < 50 bpm.
13. History of serious allergic reactions to the study drugs or excipients used in the protocol.
14. Women who are pregnant or lactating.
15. Prior use of an oral selective estrogen receptor degrader (SERD).
16. Subjects who use drugs or herbal supplements known to be moderate/strong inhibitors of CYP3A2 weeks prior to the first study drug treatment. Subjects who use drugs or herbal supplements known to be moderate/strong inducers of CYP3A4 weeks prior to the first study drug treatment.
17. Received medications which inhibits the production of stomach acid within 2 weeks or 5 drug half-lives (whichever is longer) prior to the first dose of study drugs.

18. Received medications which inhibits P-gp within 2 weeks or 5 drug half-lives (whichever is longer) prior to the first dose of study drugs.
19. Patients with active or chronic corneal disease, other active eye disease requiring ongoing treatment, or any clinically significant corneal disease for which drug-induced keratopathy cannot be adequately monitored.
20. Other conditions that the investigator considers inappropriately for this study.

